3.2 Study Population

Adult patients (≥ 18) who have AF are actively prescribed oral anticoagulant therapies (OATs) and have recently experienced bleeds, up to a maximum of 4 weeks prior to enrolment. No upper age limit will be applied, but patients must match all other inclusion/exclusion criteria (section 3.2.1). Patients will be selected from the Swansea area only, who attend/have attended either anticoagulation clinics within the Swansea City Health Cluster, Morriston emergency department or have been admitted to wards at Morriston Hospital due to a bleed.

3.2.1 *Inclusion Criteria*

- Adult patients (≥ 18 years old)
- Patients who can understand all study information and literature to provide fully informed consent
- Atrial fibrillation (AF) as the primary diagnosis
- Having a major or minor bleed up to a maximum of 30 days prior to point of enrolment
- Receiving oral anticoagulation therapy for AF

3.2.2 *Exclusion Criteria*

- Pregnant women
- Patients with active cancer
- Patients unable to consent for themselves
- Patient on concomitant antiplatelet therapy

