- A sub-set of 10 patients will be asked to take part in a qualitative semi-structured interview, which will aim to further describe patient QoL after a bleed, while anticoagulated. Patients completing the interview will also be asked to provide any comments and opinions regarding the suitability of the chosen study PROMs for properly capturing all QoL issues after a diagnosis of AF.

Study Population:

Primary and secondary care patients with AF (aged ≥ 18) who are actively prescribed oral anticoagulant therapies (OATs) and have recently experienced bleeds, up to a maximum of 4 weeks prior to enrolment. No upper age limit will apply but potential study participants must match all inclusion/exclusion criteria, detailed fully in section 3.2.1 & 3.2.2.

Data Collection Methods:

Data sources: Electronic and/or paper records kept at primary and secondary care will be regularly searched for identification of suitable patients. Patients routinely attending anticoagulation clinics will be asked if they have experienced a recent bleed, and those who present as eligible will be asked to take part in the study. Posters placed in appropriate locations in GP clinics will encourage patients who have AF and are anti-coagulated to discuss minor bleeds with GPs. Lastly, e-cards will be sent out to patients with AF groups on forums, social media pages, web site and newsletters run by online AF support networks.

Exposure: Anticoagulated to prevent stroke following diagnosis of AF.

Data collection: Data will be obtained using questionnaires supplied on paper case report forms or via an electronic device, depending on participants' preference and up to date restrictions due to coronavirus outbreak in regards to using touchscreen devices. Data captured via an electronic device will be submitted directly to a REDCap database which has been designed for the study. Completed paper versions of the survey will later be transcribed into the database by a member of the study team. A random subset of enrolled AF patients will also undergo recorded interviews with research nurses in order to capture valuable free-form, emotive data regarding effect on quality of life after a bleed and to document patient opinion on current available PROMs used in the study.

Data Analyses:

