3 STUDY DESIGN

3.1 Overview of Study Design

A descriptive evaluation of the QoL of patients with AF experiencing a bleed, both in primary care and secondary care settings (hospital wards and the emergency department (ED)).

Patient Recruitment & Study Sites

All patients will be targeted based on strict inclusion and exclusion criteria, as detailed further below (Section 3.2.1 & 3.2.2). Recruitment strategies will vary considerably in order to limit unconscious recruitment bias (for example, taking care not to direct all efforts only towards those patients who are more disposed to seek medical care when experiencing bleeds). Initially, eligible patients will be identified from regular searches in secure databases in both primary (GP surgeries) and secondary care

(ward/emergency department [ED]). JCRF staff will provide recruitment support by regular screening of A&E databases at Morriston hospital. Letters of invite will be sent out to patients who appear eligible via secondary care. NO on-site visits will take place by JCRF staff due to restrictions surrounding COVID-19 and social distancing. Patients will be subsequently approached about the study by means of a face-to-face referral in clinics where viable, in line with current consultation arrangements during the COVID-19 period, or, alternatively, study information will be posted to capture patients with AF who may not have recently visited clinics, wards, or emergency department (ED). Where appropriate, study posters will be placed in optimal locations such as general practice (GP) clinics to display information about the study, in lay terms, to encourage discussion with GPs concerning all recent minor bleeds (as defined by ISTH32), which the patient may not have thought relevant enough to mention otherwise. Leaflets and study cards will be provided, which will allow potential participants to take away study information for consideration, including by friends and family members. Patients interested in participating in the study will be instructed to contact the clinical research team directly to streamline screening and enrolment process, and to limit time burdens on healthcare staff.

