Based on data provided by anticoagulation clinics within the Swansea City Health Cluster (eight general practices in the Swansea area), it is estimated that there are approximately 500 patients with AF who are currently taking prescribed anticoagulants. All eligible patients identified within the Health Cluster, will be contacted via post and, if willing, asked to report on any bleeds within the recruitment period. A further recruitment drive will take place synchronously in hospital settings, where all patients who attend the emergency department (ED) of Morriston Hospital or admitted to the wards due to bleeds, will be approached for participation in the study. These patients will be identified following admission, but existing in-patients at study outset will be approached if it is appropriate to do so. Lastly, e-cards will be sent to specific patient groups as required, on forums, social media, web site and newsletters run by online AF support networks. Finally, patients will be informed of the study via online AF support groups on forums, social media pages and from a large database of patients, managed by the support group. Approximately 60,000 patients are held on the database in total, which will be accessed and filtered to identify eligible AF patients. Consent will be received digitally and an online link to the questionnaires will be sent to those who wish to participate. Follow-up data collection for these patients will also be conducted digitally.

Recruitment is anticipated to commence in September 2020 and will continue for 6 months – a key decision made in light of the COVID-19 outbreak. Although the study will aim to recruit between 50 and

80 patients in the first instance, all suitable patients who are willing to partake in the study will be included. A maximum of 200 patients will be permitted to enroll if successfully screened.

The research team will not have any contact with the patient unless the patient registers their interest in the study or if they reply following invitation from the healthcare provider.

Screening & Enrolment

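### Section 3.2 limits selection to named Swansea sites while 3.1 also enrols through online AF networks, so the success count of 50 depends on which section is followed; the count is also pooled across settings

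*Protocol*

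**What the plan says.** Section 3.2 of the protocol closes its description of the population with a geographic and site limit: "Patients will be selected from the Swansea area only, who attend/have attended either anticoagulation clinics within the Swansea City Health Cluster". The sentence goes on to name the Morriston emergency department and admission to Morriston wards because of a bleed. No other source is listed there.

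Other parts of the protocol include an online route. Under Data Collection Methods the synopsis says that "e-cards will be sent out to patients with AF groups on forums, social media pages", and 3.3 (Data sources) repeats this. Section 3.1 adds a support-group database: "Approximately 60,000 patients are held on the database in total, which will be accessed and filtered to identify eligible AF patients". These people are enrolled, not merely informed: "Consent will be received digitally and an online link to the questionnaires will be sent to those who wish to participate", and "Follow-up data collection for these patients will also be conducted digitally".

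On eligibility, 3.1 says "All patients will be targeted based on strict inclusion and exclusion criteria, as detailed further below (Section 3.2.1 & 3.2.2", and the synopsis says "potential study participants must match all inclusion/exclusion criteria, detailed fully in section 3.2.1 & 3.2.2". Neither of those two lists contains a residence or site criterion.

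The synopsis sets success at a minimum of 50 recruited, and 4.1 sets the recruitment criterion at 50 patients who are eligible. Section 4.1 also requires retention of at least half of those enrolled. None of these is split by setting or source. Section 3.4 lists recruitment pathway among the variables to be collected and reported descriptively.

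**The concern.** The main pass/fail rule is a head count. A recruit from outside the named sites is enrolled under 3.1 but lies outside the population in 3.2, so two people applying the protocol in good faith could count differently.

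The second issue stands even if everyone agrees on who counts. Section 2.1 ties measuring QoL to primary and secondary care, and section 5 names prompt identification of patients in those settings as an open uncertainty. A single pooled 50 could be reached mainly through online networks. The rule would then be met without showing that the clinical settings can supply and evaluate such patients, which a larger study would need to know.

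**Working it through.** There is no calculation in the plan to reproduce. The 50 to 80 range rests on cited pilot-study guidance, with no precision target or power. The check is a comparison of passages plus simple counting.

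**1. One test case.** Take a consenting adult with AF as primary diagnosis, on an oral anticoagulant, with a recent bleed and no exclusion, who lives outside Swansea and joined through a support network.
- Section 3.2.1: meets every inclusion criterion.
- Section 3.2.2: meets no exclusion criterion.
- Section 3.1: consented, surveyed and followed digitally.
- Last sentence of 3.2: not in the study population.

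The first three cannot be reconciled with the fourth for this person. If the database filter in 3.1 were meant to include the Swansea limit, the conflict would disappear for database recruits, but no such filter is stated.

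**2. When the pass/fail answer changes.** Let T be the total enrolled and X the number from outside the 3.2 sites. The count is T if 3.1 is followed and T − X if 3.2 is followed. The two disagree on success when T ≥ 50 and T − X < 50, that is, when X > T − 50.
- T = 50: X of 1 or more.
- T = 80 (top of the planned range): X of 31 or more.
- T = 200 (the cap): X of 151 or more.

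The protocol gives no expected X, so these are thresholds, not predictions.

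**3. What a pooled 50 can contain.** Let s be the share of recruits not identified through primary or secondary care. The protocol does not give s, so the values below are assumptions. Recruits from the clinical settings number 50 × (1 − s):
- s = 0: 50
- s = 25%: 37.5
- s = 50%: 25
- s = 75%: 12.5
- s = 100%: 0

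To have 50 from the clinical settings, total enrolment must be 50/(1 − s), rounded up: 67 at 25%, 100 at 50%, and 200 at 75%. The last equals the protocol's cap.

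**4. The stated pools.** For the Health Cluster, "it is estimated that there are approximately 500 patients with AF who are currently taking prescribed anticoagulants". Reaching 50 from the cluster alone therefore means 50/500 = 10% of them with an eligible bleed and consent, and 80 means 80/500 = 16%. Hospital flow is not given. The database total of about 60,000 is before any filtering. It would hold as many anticoagulated AF patients as the cluster if 500/60,000 = 0.83% of its members were such patients. These are pool sizes. Response by route is not given, and some members may attend the named sites.

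**The case against.** The strongest reply is that the counting question is nearly settled. Both the synopsis and 3.1 send the reader to 3.2.1 and 3.2.2 for the criteria, neither list has a site rule, and 3.1 says that all suitable and willing patients will be included. On that reading, one sentence in 3.2 is out of step with the rest. This largely stands: the text favours counting online recruits. But the sentence sits in the section that defines the population, and it says the opposite.

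Four stronger readings are tempting and not supported:
- A reader might infer that 3.3 contradicts itself, because its case-identification sentence lists only clinics, ward records and emergency department records. That list is not worded as exclusive, and the same section names e-cards to online networks. It needs alignment, no more.
- A reader might infer from 60,000 against 500 that the online route will dominate. The first figure is unfiltered, the second is already restricted to anticoagulated AF patients, and no yields are given.
- A reader might infer that recruitment by route will go unreported. Section 3.4 commits to reporting it descriptively, and a statistical analysis plan may add tables. What is missing is a link to the criteria in 4.1.
- A reader might infer that the plan treats 50 as proof of feasibility in each setting. No passage says so. In 2.1 the settings are attached to measuring QoL, not to recruiting, and the first feasibility question names no setting. The synopsis wording is looser. The limitation is that the pooled count cannot show setting-specific feasibility by itself.

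**Conclusion.** The conflict between 3.2 and 3.1 is present in the current text and should be fixed before recruitment. Confidence is high about the wording and does not extend to the effect on the result: X and s are unknown, so the change in the count cannot be computed. It is nil if no one from outside the named sites enrols, and decisive if X exceeds T − 50.

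The pooled-criterion point is a limit on interpretation. It does not make 50 a wrong number, and the documents give no basis for a minimum per setting.

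As a side note that adds no weight here, the bleed window is 4 weeks in the synopsis and the opening of 3.2, but 30 days in 3.1 and 3.2.1. The difference is 30 − 28 = 2 days, and the passages must be reconciled.

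**What to change.** 1. Reconcile the last sentence of 3.2 with 3.1, and align the case-identification sentence in 3.3.
2. State in 4.1 and the synopsis, before recruitment starts, whether recruits from outside the 3.2 sites count toward the 50.
3. In 3.4, define the recruitment pathway categories. Say how to classify a patient reached by more than one route, and an online recruit who attends a named site. Route and care setting are not the same thing, and the variable has no stated categories.
4. Show the recruitment and retention criteria by pathway beside the pooled figures.
5. Base conclusions about primary and secondary care only on recruits identified through those settings.
6. Separately, reconcile the two bleed windows.

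The cost is wording in the synopsis, 3.2, 3.3, 3.4 and 4.1, with Trial Steering Committee agreement for 4.1. The pathway variable is already to be collected; only its categories need defining. Invitation and response denominators by route would be useful but need a log that the protocol does not describe, so they are optional.

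The downside is that figures by setting may look less favourable than the pooled one and are less precise. As an illustration, 50% retention has an exact (Clopper-Pearson) 95% interval of 35.5% to 64.5% at 25/50, but 24.7% to 75.3% at 8/16, about a third of that sample.

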3.3 Data Source/Data Collection Process

Data sources

As part of this feasibility study, we will explore the most appropriate mechanism to identify patients who have experienced recent minor and major bleeds. We will extend recruitment across both primary and secondary care, including wards and the ED. Patients attending anticoagulation clinics at the Swansea City Health Cluster (made up of eight separate general practices) will be identified by the practice pharmacist or nurse. They will be given information about the study and will consent for a research nurse to contact them to complete the study questionnaires. Research nurses based in Swansea University's Joint Clinical Research Facility (JCRC) will undertake regular exploration of Morriston Ward F audit data (Stroke ward) to identify patients who have experienced a recent bleed. Our GP investigator will also identify patients from ED records at Morriston hospital. Lastly, e-cards will be sent to specific patient groups on forums, social media, web site and newsletters, which are run by online AF support networks.

Outcomes

Quality of life and the impact of the anticoagulation treatment will be collected via validated patient-reported outcome measures (PROMs). We will also include a small number of additional relevant questions regarding when the bleed occurred, the nature of the bleed, and current treatment for the patient. We will also collect the documented cause and location of bleed as identified in discharge summary (for secondary care) in patients with major bleeds. Patient reported bleeds will be posthumously classified into minor or major bleeds by a clinician.

Exposure

Oral anticoagulant to prevent stroke following diagnosis of AF.

Data collection

Cases will be identified from i) routine anticoagulation clinics in primary care, ii) from hospital records for ward patients and from ED records. QoL data will be collected directly from patients via questionnaires. We envisage that data will be collected from patients via an electronic tool, ideally via patients' phones or tablets. We will also produce paper versions of questionnaires for patients who do not have access to a smartphone/tablet or would prefer this method of questionnaire completion. In order to maximise data collection, we will collect data directly from patients attending primary or secondary care if feasible or by phone or post.

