3.4 Definitions of Study Variables

As defined by the International Society for Thrombosis and Haemostasis^{2 32} for non-surgical patients

Major bleed

1. Symptomatic bleeding in a critical area or organ, such as intracranial, intraspinal, intraocular, retroperitoneal, intraarticular, or pericardial, or intramuscular with compartment syndrome.

2. Bleeding causing a fall in hemoglobin level of 2 g/dL (1.24 mmol/L) or more, or leading to transfusion of two or more units of whole blood or red cells.

Minor bleed

All non-major bleeds will be considered minor bleeds. Minor bleeds will be further divided into those that are clinically relevant and those that are not. Some examples of minor bleeds include but not limited to:

- Nose bleeds
- Bloody stools
- Small, manageable cuts (e.g shaving cuts)
- Noticeable and/or persistent bruising

Clinically Relevant Minor Bleed

A clinically relevant minor bleed is an acute or subacute clinically overt bleed that does not meet the criteria for a major bleed but prompts a clinical response, in that it leads to at least one of the following:

- A hospital admission or attendance at A&E for bleeding, or
- A physician guided medical or surgical treatment for bleeding, or
- A change in antithrombotic therapy (including interruption or discontinuation of oral anticoagulant).

Other variables collected in the study will be the following:

- Recruitment pathway
- Medication type
- Co-morbidity/ies, if present
- Location of bleed
- Impact of COVID-19 pandemic and resulting restrictions and closures on ability to seek medical care for a bleed

Collecting the above confounding variables, each of which also has the potential to have some impact on QoL for patients with AF who experience bleeding (while anticoagulated), will allow researchers to reflect on and account for any resulting confounder bias. Confounding variables will be reported on within the end of study descriptive analysis.

3.4.1 *Outcomes/Endpoint Variables*

Quality of life data and the impact of the anticoagulation treatment will be collected via validated patient-reported outcome measures (PROMs). We will also include a small number of additional relevant questions regarding when the bleed occurred, the nature of the bleed and their current treatment. We will also collect the documented cause and location of bleed as identified in discharge summary (for secondary care) in patients with major bleeds.

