4 STATISTICAL ANALYSIS

Due to the feasibility aspect of the study and the low number of cases, a full statistical analysis is not planned. A descriptive analysis of QoL reported by AF patients following a minor and/or major bleed, while anticoagulated, will be performed. Patients who experience multiple bleeds over the course of study participation and consequently report these to research staff will be included, and multiple bleeds will be posthumously categorised into minor or major bleeds by a clinical professional and included as part of the descriptive analysis. Recorded treatment type (anticoagulant used) will be compared with type of bleed (minor/major) to determine if there is any possible linkage which could warrant further testing. Comparison to age-adjusted population norms may be insightful but no comparisons with controls are planned for this feasibility assessment.

A brief thematic analysis (Braun and Clarke, 2006)³³ will be conducted on transcribed interview data, to draw out important common themes relating to the study question, which will not be directly captured through the chosen PROMs. Specific qualitative data analysis software, NVivo 12, will be used for additional insight and to identifying trends in unstructured data captured during study interviews.

Lastly, CRF's and online survey links will include sections for eligible patients to provide open-ended feedback regarding each of the PROMs used in this study and how far the PROM captured bleed-specific QoL issues for anticoagulated AF patients. As previously stated, this information will not be used to

conduct a full statistical analysis but will allow researchers to gauge each PROM performance in capturing QoL post-bleed(s) for these patients.

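### The protocol asks for current treatment, not the drugs taken at the bleed, and leaves the antiplatelet exclusion undated, so a bleed may be set against the wrong regimen

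*Protocol*

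**What the plan says.** Of the criteria that concern the bleed and the drugs, only the bleed is dated. Section 3.2.1 requires "Having a major or minor bleed up to a maximum of 30 days prior to point of enrolment", while the opening paragraph of section 3.2 puts the limit at "up to a maximum of 4 weeks prior to enrolment". The two drug criteria carry no date: the inclusion reads "Receiving oral anticoagulation therapy for AF" and the exclusion in section 3.2.2 reads "Patient on concomitant antiplatelet therapy".

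Under Outcomes, section 3.3 adds a few questions on "when the bleed occurred, the nature of the bleed, and current treatment for the patient". Section 3.4.1 repeats them in almost the same words. Section 3.4 also lists medication type, undated, among the confounding variables. The synopsis, under secondary outcome measures, has patients supply their anticoagulant information together with the details of the bleed, before they fill in the questionnaires. Section 3.1 has the first questionnaires completed straight after consent.

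One of the clinical responses that make a minor bleed clinically relevant under section 3.4 is: "A change in antithrombotic therapy (including interruption or discontinuation of oral anticoagulant". Section 4 then plans: "Recorded treatment type (anticoagulant used) will be compared with type of bleed (minor/major". The aim is to see whether a link is worth testing later.

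**The concern.** The comparison in section 4 is informative only if the drug in the table is the one the patient was taking when the bleed happened. The data items that carry an explicit time ask for something else, namely treatment at the time of asking. If the regimen changed in between, the bleed may be set against a drug started because of it. Switching is then a consequence of the bleed, so the error could depend on severity, which is the other axis of the same table. A link could appear, or be hidden, through switching alone.

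The undated exclusion raises the same question of timing. The primary objective (section 2.1) concerns bleeds that result from anticoagulant treatment. A patient who bled on an anticoagulant plus an antiplatelet, and stopped the antiplatelet before enrolment, can be read as meeting every criterion.

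A later analysis plan cannot repair this: it cannot recover a bleed-date drug that was never asked for, nor change who was enrolled.

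**Working it through.** The check is mainly textual: it compares the time to which each item refers.

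| Item | Where | Refers to |
|---|---|---|
| Qualifying bleed | 3.2, 3.2.1 | up to 30 days, or 4 × 7 = 28 days, before enrolment |
| Receiving an anticoagulant | 3.2.1 | no date |
| On an antiplatelet | 3.2.2 | no date |
| Added drug question | 3.3, 3.4.1 | treatment now |
| Medication with bleed details | Synopsis | taken before the questionnaires; no date for the drug |
| Medication type | 3.4 | no date |
| Therapy change after a bleed | 3.4 | between bleed and data collection, foreseen |
| Anticoagulant against bleed type | 4 | needs the drug at the bleed; not stated |

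1. Medication is recorded before the questionnaires (synopsis), and the first set follows consent (section 3.1). The drug answer is therefore taken at enrolment, up to 28 or 30 days after the bleed. The point holds under either limit.
2. Section 3.4 itself foresees the regimen changing, being interrupted or being stopped because of a bleed. The drug now and the drug at the bleed can therefore differ.
3. No section asks for the drug at the bleed or for any later switch. Section 3.3 takes only cause and location from discharge summaries, and only for major bleeds, so that source does not fill the gap.
4. Section 4 also includes further bleeds reported during participation. A single entry for current treatment cannot be matched to each of them.

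Size: the documents give no rate of antiplatelet use, stopping or switching. For illustration only, let p be the share of otherwise eligible bleeders on an antiplatelet at the bleed, and s the share of those who stop before enrolment. Assume that no one starts one after the bleed and that the exclusion is applied by status at enrolment. The share of the eligible pool that bled on combined therapy is then p·s / (1 − p + p·s). With s assumed to be one half:

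- p = 5%: 2.5 / (95 + 2.5) = 2.6%
- p = 15%: 7.5 / (85 + 7.5) = 8.1%
- p = 25%: 12.5 / (75 + 12.5) = 14.3%

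All these inputs are assumptions, and s was not varied. For the drug table no formula adds anything, since the share that could be misplaced is simply whatever share had switched.

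**The case against.** The text can be read more kindly. The synopsis pairs medication with the bleed, section 4 speaks of the anticoagulant used and not the current one, and the treatment question may be meant to cover treatment of the bleed. The word concomitant could mean at the time of the bleed. The case report form is not shown and may ask the right question. This stands as far as it goes: the text is ambiguous, and misplacement may happen but is not certain. It does not close the gap, because the two sections that put a time on the drug question both say current, and different staff and online respondents could apply different dates.

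A reader might infer that the exclusion is expressly tied to enrolment, so that patients on combined therapy are bound to enter. It is undated, and its purpose is not stated. A reader might also infer that the error falls mainly on major bleeds. No passage supports that: the only mention of therapy change is in the definition of a clinically relevant minor bleed.

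An enrolment reading also has a rationale. AFEQT and PACT-Q Part 2 are completed at enrolment and ask about treatment effects, burden and satisfaction, on which current co-medication bears. Moving the exclusion wholly to the bleed date would admit patients taking an antiplatelet when they answer. That objection stands and shapes the fix.

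Finally, section 4 plans no full statistical analysis, and recruitment, retention and questionnaire completion do not depend on the drug attributed to a bleed. That limits the weight of the point.

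**Conclusion.** The point holds in a limited form. As written, the protocol does not secure the drug taken at the bleed, although it foresees regimens changing after a bleed and plans a comparison that needs the earlier one. A switched patient may be tabulated under a drug that did not precede the bleed, and a patient who bled on combined therapy can be read as eligible.

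The size cannot be calculated from the documents; the 2.6% to 14.3% range only shows how the leak would scale under assumed inputs. What is affected is a secondary, hypothesis-generating comparison, the use of medication type as a confounder, and the premise that the bleeds result from anticoagulant treatment. The minimum of 50 recruits and the other progression criteria are not touched. It is worth correcting because it is cheap to correct before data are collected and cannot be recovered reliably afterwards.

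**What to change.** - **Case report form and online survey:** record the anticoagulant and any antiplatelet on the date of the qualifying bleed, and on the date of any later reported bleed, as well as current treatment. Bring the wording of sections 3.3 and 3.4.1 into line.
- **Section 4:** state that the comparison with bleed type uses the bleed-date anticoagulant. Keep current treatment as a descriptor.
- **Section 3.2.2:** state the reference date of the antiplatelet exclusion so that it covers use at the qualifying bleed in addition to, not instead of, use at enrolment. Alternatively, leave eligibility as it is and flag in the descriptive analysis the patients who were on an antiplatelet at the bleed.
- **Section 3.2:** reconcile the 4-week and 30-day limits, since they set the longest recall period.

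The cost is an added medication item, a few words in section 3.2.2 and a line in section 4. Patients must recall their regimen over at most 30 days for the qualifying bleed, a window over which they already recall the bleed itself. If the exclusion is widened, a few fewer patients may be eligible; flagging avoids that loss.
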